## **Confidentiality Statement**

Final 2.0 Amendment 1.0, 22-May-2017

Page 104 of 106

Related to PMI\_RD\_WKI\_000759

CSP	

Short-Acting Beta Agonists	6 hours prior to spirometry	
	(except as per protocol before	
	spirometry)	
Long-Acting Beta Agonists	3 days before Visit 1 until Visit	
	2	
Phosphodiesterase 5 inhibitors (i.e. Sildenafil, Vardenafil, Tadalafil)	7 days before Visit 1 until Visit	
	2	
Amiloride	3 days before Visit 1 until Visit	
	2	
	7 days before Visit 1 until Visit	
Macrolide antibiotics	2	
	3 days before Visit 1 until Visit	
Guaifenesin	2	
	14 days before Visit 1 until	
Mucolytic agents	Visit 2	
	14 days before Visit 1 until	
Topical menthol products	Visit 2	
opical nasal medication	4 weeks before Visit 1 until	
	Visit 2	
	4 weeks before Visit 1 until	
Topical ocular medication		
	Visit 2	
Any other medication at the Principal Investigator or designee's	As per Principal Investigator or	
discretion that might interfere with the endpoints or procedures.	designee.	

#### **Confidentiality Statement**

P1-CMS-01-US

Final 2.0 Amendment 1.0, 22-May-2017

Page 105 of 106

Related to PMI\_RD\_WKI\_000759

CSP

11. Subjects with evidence of COPD, Global Initiative for Chronic Obstructive Lung Disease (GOLD) stage I or greater, and a forced expiratory volume 1 / the forced vital capacity ratio (FEV 1 /FVC ratio) <0.7.	Х	
12. Any condition the Principal Investigator or designee has cause to believe would interfere with the procedures for upper or lower airway function. This could include, but is not limited to, nasal/septum deviations, or nasal polyps or nasal allergies which will be identified by the Principal Investigator or designee.	Х	Х
13. Upper or lower respiratory diseases in the 4 weeks prior to Visit 2.	Х	Х
14. History of nasal or sinus surgery in the 5 years prior to Visit 2.		Х
15. As per the Principal Investigator or designee's judgment, the subject has medical conditions which require or will require in the course of the study, a medical intervention (e.g., start of treatment, surgery, hospitalization) which may interfere with the study participation and/or study results.	Х	
16. The subject has a positive alcohol test and/or a history of alcohol abuse that could interfere with the subject's participation in study at Visit 1 or Visit 2.	Х	Х
17. Positive urine drug screen at Visit 1 or Visit 2.	Х	Х

#### **Confidentiality Statement**

CSP

P1-CMS-01-US

Final 2.0 Amendment 1.0, 22-May-2017

Page 106 of 106

Related to PMI\_RD\_WKI\_000759

 
The subject has positive serology test for human immunodeficiency virus (HIV)1/2, Hepatitis B or Hepatitis C.
 
		Х
19. Subject has donated or been in receipt of whole blood or blood products within 3 months prior to Visit 1.	Х	
20. Subject is a current or former employee of the tobacco industry or of their first-degree relatives (spouse, legal patner, parent, sibling, and child).	Х	
21. Subject is an employee of the investigational site or any other parties involved in the study or of their first-degree relatives (spouse, legal patner, parent, sibling, and child).	Х	
22. Subject has been in receipt of last dose from another clinical study within 3 months prior to Visit 1.	Х	
23. Subject has been previously screened in this study.	Х	

### 1 INTRODUCTION

This Statistical Analysis Plan (SAP) was written in accordance with Eurotrials' Standard Operating Procedures (SOP) ST.CO.01-01 for Biostatistics and intends to provide guidelines from which the analysis will proceed, create a common and clear understanding of the planned analysis by all involved, clarify issues which was not clarified in the protocol, expand statistical section of the protocol, provide basis for the statistical section of the statistical report and reduce the opportunity for bias by prospectively defining analysis. This SAP was prepared by the biostatistician who will be further responsible (if possible) for the statistical analysis of the study data.

This SAP, in particular table shells and examples of figures/graphs, was reviewed and approved by the Sponsor's Representative previously to database locking and performance of the statistical analysis.

Any changes to the planned statistical methodology/definitions described on this SAP during the statistical analysis of the study data will be documented in the Statistical Report.

This document was written in accordance with the information contained in the Study Protocol 15-LE-001-RD, Version Final 1.0 of 08-Dec-2016 and eCRF version Final V1.0 of 12Jan2017.

### 2 STUDY OBJECTIVES AND ENDPOINT

#### 2.1 Primary objectives and endpoints

The primary objectives of this study are:

1. To evaluate the NMC over the course of 12 hours following single use of cigarette in smokers.

• STT value as assessed by STT test at each time point.

2. To compare NMC over the course of 12 hours in smokers following single use of cigarette relative to never smokers.

• STT value as assessed by STT test at each time point.

3. To examine the relationship between plasma nicotine levels and STT value in smokers and never smokers.

• STT value as assed by the STT test and plasma nicotine levels at each time point.

### 2.2 Secondary objectives and endpoints

The secondary objectives of this study are:

- 1. To standardize nasal scraping procedure using two methods.
- Collection of nasal epithelium for further histology.
- Evaluation of RNA quality and quantity.

- 2. To monitor the safety during the study.
- Vital signs.
- Adverse events (AE).
- Nasal and throat exam.
- Hematology, clinical chemistry and urine analysis.
- Brief physical examination.
- Concomitant medications.

### **3 STUDY DESIGN**

This will be a single-center study in which 14 healthy adult male study participants, consisting of 7 cigarette smokers and 7 never smokers as a control group, will be enrolled. Study participants will not be replaced after being enrolled.

This study will have three visits on three separate days as described in Figure 1.

Figure 1 – Study flow chart

### 4 STUDY POPULATION

#### 4.1 Inclusion criteria

1. Informed of the nature of the study and have agreed to and are able to read, review, and sign the informed consent form (ICF) prior to Screening. The subject must be willing to comply with the study procedures described in the informed consent. The informed consent document will be written in English, therefore the volunteer must have the ability to read and communicate in English.

2. Male subject aged  $\geq$ 25 to  $\leq$ 40 years old.

3. BMI between 18.0 kg/m^2 to 32.0 kg/m^2, inclusive.

4. Judged by the Principal Investigator or designee to be in good health as documented by the medical history, physical examination, vital sign assessments, clinical laboratory assessments, and by general observations.

5. Belong to one of the following two groups:

a. Non-menthol cigarette smoker (meets all of the following criteria at Visit 1 and at Visit 2):

i. A positive urine cotinine test ( $\geq$ 200 ng/mL).

- ii. Smoked at least 20 cigarettes per day for at least the past 5 years.
- iii. eCO levels >10 parts per million (ppm).
- iv. No plans to quit smoking in the next 3 months.
- b. Never smoker (meets all of the following criteria at Visit 1 and at Visit 2):

i. Subject who has smoked less than 100 cigarettes throughout their lifetime and no cigarettes in the past 3 years.

- ii. A negative urine cotinine test (<200 ng/mL).
- iii. eCO levels ≤ 5 ppm.

6. Completed the Screening process within 30 days prior to Visit 2.

7. Availability for the entire study period and willingness to comply with study procedures, including smoking interruptions, as evidenced by a signed ICF and at Visit 2.

### 4.2 Exclusion criteria

1. As per the Principal Investigator or designee's judgment, the subject cannot participate in the study for any reason (e.g., medical, psychiatric, and/or social reason).

2. Subject is legally incompetent, or physically or mentally incapable of giving consent (e.g., emergency situation, under guardianship, prisoners, or subjects who are involuntarily incarcerated).

3. Presence of confounding allergies including allergic rhinitis and non-allergic rhinitis during the course of the study based on medical history and SPT.

4. Clinical significant abnormality on their nasal and throat exam, at the discretion of the Principal Investigator or designee at Visit 1 and/or at Visit 2.

5. Cigarette smoker who smoke/use any tobacco or nicotine products (other than CC), such as cigars, pipe, menthol cigarettes or electronic cigarettes in the previous 3 months, as self-reported at Visit 1 or Visit 2.

6. Never smoker who smoke/use any tobacco or nicotine products, such as cigars, pipe, menthol cigarettes or electronic cigarettes in the previous 3 years, as self-reported at Visit 1 or Visit 2.

7. Cigarette smokers who state they will be unable to abstain from smoking for up to 24 hours.

8. Inability to taste sweet within 60 minutes in the STT test.

9. Subjects who routinely use or who have used in the previous 4 weeks nasal sprays, inhalers or other nasal products, such as nasal irrigation (for example, Neti Pot) prior to Visit 1 and/or Visit 2.

10. Subjects who have taken any of the following medication without the indicated minimum washout period:

Prohibited Medication	Restriction period (with Principal Investigator or designee discretion)
Short-acting antihistamines including intranasal antihistamines	3 days before Visit 1 until Visit 2
Long-acting antihistamines (i.e. Loratadine, Desloratadine)	7 days before Visit 1 until Visit 2
Over-the-counter cough and cold preparations or sleep aids containing antihistamines	3 days before Visit 1 until Visit 2
Leukotriene inhibitors	14 days before Visit 1 until Visit 2
Oral or intra-articular steroid	30 days before Visit 1 until Visit 2
Intranasal and inhaled corticosteroids	14 days before Visit 1 until Visit 2
Use of monoamine oxidase inhibitors	14 days before Visit 1 until Visit 2
Decongestants	48 hours before Visit 1until Visit 2
Cromolyn products	14 days before Visit 1 until Visit 2
Beta-adrenergic blockers (i.e. Acebutolol, Atenolol, etc.)	14 days before Visit 1 until Visit 2
Anticholinergies	7 days before Visit 1 until Visit 2
Herbal or natural product remedies for allergy symptoms	On the day of Visit 1 until Visit 2
Short-Acting Beta Agonists	6 hours prior to spirometry (except as per protocol before spirometry)
Long-Acting Beta Agonists	3 days before Visit 1 until Visit 2
Phosphodiesterase 5 inhibitors (i.e. Sildenafil, Vardenafil, Tadalafil)	7 days before Visit 1 until Visit 2
Amiloride	3 days before Visit 1 until Visit 2
Macrolide antibiotics	7 days before Visit 1 until
Guaifenesin	Visit 2 3 days before Visit 1 until Visit 2
Mucolytic agents	14 days before Visit 1 until Visit 2
Topical menthol products	14 days before Visit 1 until Visit 2
Topical nasal medication	4 weeks before Visit 1 until Visit 2
Topical ocular medication	4 weeks before Visit 1 until Visit 2
Any other medication at the Principal Investigator or designee's discretion that might interfere with the endpoints or procedures.	As per Principal Investigator or designee.

Table 1 – Prohibited medication.

11. Subjects with evidence of COPD, Global Initiative for Chronic Obstructive Lung Disease (GOLD) stage I or greater, and a forced expiratory volume 1 / the forced vital capacity ratio (FEV1/FVC ratio) <0.7.

12. Any condition the Principal Investigator or designee has cause to believe would interfere with the procedures for upper or lower airway function. This could include, but is not limited to, nasal/septum deviations, or nasal polyps or nasal allergies which will be identified by the Principal Investigator or designee.

13. Upper or lower respiratory diseases in the 4 weeks prior to Visit 2.

14. History of nasal or sinus surgery in the 5 years prior to Visit 2.

15. As per the Principal Investigator or designee's judgment, the subject has medical conditions which require or will require in the course of the study, a medical intervention (e.g., start of treatment, surgery, hospitalization) which may interfere with the study participation and/or study results.

16. The subject has a positive alcohol test and/or a history of alcohol abuse that could interfere with the subject's participation in study at Visit 1 or Visit 2.

17. Positive urine drug screen at Visit 1 or Visit 2.

18. The subject has positive serology test for human immunodeficiency virus (HIV)1/2, Hepatitis B or Hepatitis C.

19. Subject has donated or been in receipt of whole blood or blood products within 3 months prior to Visit 1.

20. Subject is a current or former employee of the tobacco industry or of their first-degree relatives (spouse, legal patner, parent, sibling, and child).

21. Subject is an employee of the investigational site or any other parties involved in the study or of their first-degree relatives (spouse, legal patner, parent, sibling, and child).

22. Subject has been in receipt of last dose from another clinical study within 3 months prior to Visit 1.23. Subject has been previously screened in this study.

### 5 STATISTICAL METHODS

### 5.1 Sample size

This is an exploratory study. This study will include 14 study participants: 7 cigarette smokers and 7 never smokers. No formal powering has occurred. However, with an expected standard deviation of 2.5 minutes, a difference in STT of 3.75 minutes can be detected.

### 5.2 Statistical software

The statistical analyses will be conducted through the software SAS® (version 9.4, SAS Institute Inc, Cary).

### 5.3 Analysis datasets

#### 5.3.1 Full Analysis Set (FAS)

All study participants who have at least one evaluable STT test at Visit 3 will be included in FAS population.

#### 5.3.2 Per Protocol (PP) Population

All study participants in Full Analysis Set who have no major protocol deviation will be included in the PP population.

### 5.3.3 Safety Population

All enrolled subjects will be included in safety population.

#### 5.4 Study hypothesis

There are no statistical hypotheses to be tested for the primary analysis.

#### 5.5 Statistical analysis

All quantitative variables will be summarized through descriptive statistics namely mean, median, standard deviation, quartiles (Q1 and Q3) and minimum and maximum values. Qualitative variables will be summarized through number (n) and frequency distribution (%).

All descriptive analyses will be performed by smoker and never smoker group.

Statistical tests will be two-tailed considering a significance level of 5%.

#### 5.5.1 Subjects' disposition

The number of subjects included in this study will be described in this section. The number (n) and frequency distribution (%) of subjects who completed the study, subjects who discontinued the study and distribution for each study dataset will be also summarized by total, smoker and never smoker groups.

Subjects' disposition will be presented as described in **Table A 1** and listed in **Listing 1**. Protocol deviations will be listed by subject in **Listing 2**.

#### 5.5.2 Demographic and other clinical assessments

Demographics at visit 1 will be summarized by total number of observations (n), namely mean, median, standard deviation, quartiles (Q1 and Q3) and minimum and maximum values for continuous variables, and total number of observations, number (n) and frequency distribution (%) for categorical variables.

Demographics and other assessments will be presented for FAS and PP dataset as described in **Table A 2** and **Table A 3**, respectively and listed in **Listing 3**.

Smoking history, medical history, prior and concomitant medication, exhaled carbon monoxide, drug/alcohol test, skin prick test and tobacco consumption will be listed by subject in **Listing 4** to **Listing** *10*, respectively.

### 5.5.3 Primary analysis

STT for each time point will be summarized by smoker and never smoker groups using the descriptive statistics: mean, median, standard deviation, quartiles (Q1 and Q3), minimum and maximum values and 95% confidence interval (CI).

Changes in STT from T0 will be computed at T4, T8 and T12 and summarized by smoker and never smoker group using the descriptive statistics: mean, minimum, maximum, median, quartiles (Q1 and Q3), standard deviation (SD) and 95% confidence interval (CI).

The plasma nicotine levels for each time point will be summarized by smoker and never smoker group using the descriptive statistics mean, minimum, maximum, median, quartiles, standard deviation (SD) and 95% confidence interval (CI). The relationship between plasma nicotine levels and STT at each time point will be evaluated by spearman correlation as well as graphical presentation of these endpoints by time point and smoker and never smoker group.

Results regarding STT, plasma nicotine and STT versus plasma nicotine will be presented for FAS and PP dataset as described in **Table A 4** to **Table A 8** and in **Figure A 1** to **Figure A 4**. Data regarding STT test will be listed by subject in Listing 11.

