### **Evaluation Criterion:**

The evaluation criterion is the time lapse between placing the saccharin and tasting the sweetness. These times will be evaluated by the summary statistics described elsewhere.

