# **12** PLANNED STATISTICAL METHODS

# **12.1** General Considerations

Full details of the statistical analysis will be given in a Statistical Analysis Plan (SAP). Any changes to the planned statistical methods will be documented in the Clinical Study Report. The statistical evaluation will be performed using SAS®, version 9.2 or later.

STT for each time point will be summarized by smoker and never smoker group using the descriptive statistics: mean, minimum, maximum, median, quartiles, standard deviation (SD) and 95% confidence interval (CI).

The plasma nicotine levels for each time point will be summarized by smoker and never smoker group using the descriptive statistics mean, minimum, maximum, median, quartiles, standard deviation (SD) and 95% confidence interval (CI).. The relationship between plasma nicotine levels and STT at each time point will be evaluated by spearman correlation as well as graphical presentation of these endpoints by time point and smoker and never smoker group.

An overall summary of AEs will be presented by smoker and never smoker group showing the number of events and percent of study participants who experienced AEs, SAEs, severe AEs and AEs leading to study discontinuation.

RNA concentration will be summarized by method using descriptive statistics: mean, minimum, maximum, median, quartiles, standard deviation (SD) and 95% confidence interval (CI)..

RNA RIN will be summarized by method using descriptive statistics: mean, minimum, maximum, median, quartiles, standard deviation (SD) and 95% confidence interval (CI).

A summary of AEs by System Organ Class (SOC) and Preferred Term (PT) by smoker and never smoker group will be presented.

Vital signs will be summarized by smoker and never smoker group using descriptive statistics: mean, minimum, maximum, median, quartiles, standard deviation (SD) and 95% confidence interval (CI)..

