12.1.2 Significance Level for Inferential Analysis

This study has no formal pre-specified hypotheses associated with the study objectives. However, 95% CI will accompany all effect estimates.

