### 5.6 Missing values

Missing STT values for a time point will be treated as missing. When STT detection takes longer than 1 hour, the STT will be considered as 1 hour. When the subject is not able to test saccharine on direct application, the STT values should be treated as missing, and these subjects should not be included in the STT analysis.

Regarding plasma nicotine samples:

- Missing sampling time: if the time of collection for a sample is unknown, that individual data point will be treated as missing data for descriptive statistics.
- Missing concentration data: missing concentration data will be treated as missing and replaced with a "." in the concentration dataset. No values will be imputed.
- Concentration data below lower limit of quantification (LLOQ=0.399 ng/mL): in the calculation
  of descriptive statistics for concentration data at each sampling time point, all LLOQ values will
  be treated as zero for time zero and as 1/2 LLOQ for the remaining time

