### Table A 3 – Demographic and anthropometric characteristics at visit 1 – PP population

	Visit 1		Visit 2		Visit 3 –T0		Visit 3 – T4		Visit 3 – T8		Visit 3 – T12	
	Smoker (n=xx)	Never smoker (n=xx)										
STT result (min) N Mean Standard Deviation Q1 Q3 Minimum Maximum 95% Cl												
Change from T0												
N	-	-	-	-	-	-						
Mean	-	-	-	-	-	-						
Median	-	-	-	-	-	-						
Standard Deviation	-	-	-	-	-	-						
Q1	-	-	-	-	-	-						
Q3	-	-	-	-	-	-						
Minimum	-	-	-	-	-	-						
Maximum	-	-	-	-	-	-						

Table A 4 – Saccharin transit time – FAS population

STT value will be obtained as the difference between end time and start time, in minutes (see appendix 1).

	Visit 1		Visit 2		Visit 3 –T0		Visit 3 – T4		Visit 3 – T8		Visit 3 – T12	
	Smoker (n=xx)	Never smoker (n=xx)										
STT result (min) N Mean Standard Deviation Q1 Q3 Minimum Maximum 95% Cl												
Change from T0												
N	-	-	-	-	-	-						
Mean	-	-	-	-	-	-						
Median	-	-	-	-	-	-						
Standard Deviation	-	-	-	-	-	-						
Q1	-	-	-	-	-	-						
Q3	-	-	-	-	-	-						
Minimum	-	-	-	-	-	-						
Maximum	-	-	-	-	-	-						

Table A 5 – Saccharin transit time – PP population

STT value will be obtained as the difference between end time and start time, in minutes (see appendix 1).

	Visit 3 –T0		Visit 3 – T4		Visit 3 – T8		Visit 3 – T12	
	Smoker (n=xx)	Never smoker (n=xx)						
Result (%) N Mean Median Standard Deviation Q1 Q3 Minimum Maximum 95% CI								

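### Primary objective 2 compares smokers with never smokers on STT, but the plan defines no between-group difference and no confidence interval for one

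*SAP*

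**What the plan says.** Both documents give the same second primary objective: "To compare NMC over the course of 12 hours in smokers following single use of cigarette relative to never smokers" (SAP 2.1; also Protocol 3.1 and the synopsis).

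The planned STT analysis is a set of group summaries. Protocol 12.1 states that "STT for each time point will be summarized by smoker and never smoker group using the descriptive statistics", and SAP 5.5.3 repeats this as "STT for each time point will be summarized by smoker and never smoker groups using the descriptive statistics". Each group receives its own 95% CI at each time point. The SAP adds change from T0 at T4, T8 and T12, again by group. The shells for Tables A 4 and A 5 have a smoker and a never-smoker column at each time point and a block headed "Change from T0". They have no row or column for a difference between groups.

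The protocol synopsis points the same way under its evaluation criterion: "These times will be evaluated by the summary statistics described elsewhere". Both documents say that no hypothesis is to be tested. Protocol 12.1.2 then adds: "However, 95% CI will accompany all effect estimates".

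Two further statements bear on the choice of method. SAP 5.6 caps long times: "When STT detection takes longer than 1 hour, the STT will be considered as 1 hour". Exclusion criterion 8 removes people with "Inability to taste sweet within 60 minutes in the STT test".

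**The concern.** An objective to compare two groups calls for a quantity that expresses the comparison. Objective 3 has one, the Spearman correlation, with its own table. Objective 2 has none. Protocol 12.1.2 expects intervals on effect estimates, but neither document says what the effect estimate for objective 2 is. The SAP follows the protocol here, so this is a gap that the two documents share and not a contradiction between them.

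Two things are at stake. First, whoever writes the report must choose the measure after seeing the data: raw STT or change from T0, a difference in means or a rank-based one. Second, without a stated difference, readers will tend to compare the two groups' intervals by eye, and that is a misleading guide to how well the difference is known.

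**Working it through.** **Inputs.** 7 smokers and 7 never smokers, SD 2.5 minutes, difference 3.75 minutes (SAP 5.1, Protocol 12.2). Two-sided 5% (SAP 5.5). SDs of 6 (smokers) and 4 (non-smokers) from the study cited in Protocol 4.2, used as a range check. Power is not stated, so 80% is assumed. Intervals are taken to be t-based intervals for means.

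**The plan's own figure.** For two groups of 7, by normal approximation, the detectable difference is (1.960 + 0.842) × 2.5 × √(2/7) = 3.74 minutes, which matches 3.75. At 70% power it is 3.32 and at 90% it is 4.33. This suggests that a between-group difference was in mind. It does not prove it, since two uncorrelated readings in a single group of 7 give the same 3.74. The point does not depend on it.

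**What the plan produces: each group's own 95% CI.** Half-width = t(6 df) × SD/√7, with t = 2.447.
- SD 2.5: 2.31 minutes.
- SD 6: 5.55 minutes. SD 4: 3.70 minutes.

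The two intervals stop overlapping when the means differ by the sum of the half-widths:
- SD 2.5: 2 × 2.312 = 4.62 minutes.
- SDs 6 and 4: 5.55 + 3.70 = 9.25 minutes.

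**What objective 2 needs: the 95% CI of the difference.** Half-width = t × √(SD₁²/n₁ + SD₂²/n₂), with Welch degrees of freedom.

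| Case | SE | df | Half-width (min) |
|---|---|---|---|
| SD 2.5 in both, 7 and 7 | 1.336 | 12 | 2.91 |
| SDs 6 and 4, 7 and 7 | 2.726 | 10.45 | 6.04 |
| SD 2.5 in both, 6 smokers and 7 never smokers | 1.391 | 10.70 | 3.07 |
| SDs 6 and 4, 6 smokers and 7 never smokers | 2.878 | 8.51 | 6.57 |

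With 7 per group, observed differences between 2.9 and 4.6 minutes (SD 2.5), or between 6.0 and 9.2 minutes (SDs 6 and 4), would show overlapping group intervals although the interval for the difference excludes zero. The plan's own 3.75 minutes lies inside the first band.

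**Difference in change from T0.** The SD of a change is SD × √(2(1 − r)). The documents give no within-person correlation r, so a range is assumed, equal in both groups.

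| r | Half-width, SD 2.5 | Half-width, SDs 6 and 4 |
|---|---|---|
| 0.3 | 3.45 | 7.14 |
| 0.5 | 2.91 | 6.04 |
| 0.7 | 2.26 | 4.68 |

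The raw and change versions have the same precision at r = 0.5 and differ on either side of it, so which one leads matters.

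**Effect of the 60-minute cap.** Constructed samples, means 16 and 10, SD about 2.5: smokers 12.3, 13.9, 15.0, 16.0, 17.0, 18.1, 19.7; never smokers 6.3, 7.9, 9.0, 10.0, 11.0, 12.1, 13.7. Replace 19.7 by 60.
- Difference in means with Welch 95% CI: 11.76 (−3.95 to 27.47).
- Hodges-Lehmann difference: 6.0 (2.9 to 10.7), from the 9th and 41st of the 49 ordered pairwise differences, exact coverage 96.2%.

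One capped value would therefore decide the answer from means but not the rank-based one.

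**The case against.** The strongest objection is that nothing is lost. Tables A 4 and A 5 print N, mean and SD by group, for STT and for change from T0, and the Welch interval follows exactly from those three numbers. That is correct, and it is why the point falls short of a fatal flaw. It does not settle which difference the sponsor regards as the answer to objective 2.

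A second objection is that the study is exploratory and unpowered and declares a descriptive method, so side-by-side summaries are a minimal but specified comparison, and any later change must be documented. The right to describe stands. But an estimated difference with an interval is itself descriptive, and Protocol 12.1.2 already expects intervals on effects.

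A third is that neither document proposes to judge by overlapping intervals, and that asking whether an interval excludes zero is testing by another name. This is fair as far as the plan's wording goes. The overlap figures show how readers could be misled by the planned display. They are not a decision rule.

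A fourth is that the remedy yields seven differences (four levels and three changes) in two populations, 14 intervals in all, with no leading one and no single 12-hour summary. This stands in part. The remedy fixes what is reported, not what is emphasised.

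Finally, the cap illustration is artificial: a value of 60 lies (60 − 16)/2.5 = 17.6 SDs above the smoker mean. Exclusion 8 makes such a value unlikely at Visit 3, though not impossible. The illustration supports only a contingency rule.

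**Conclusion.** The concern holds and should be fixed. The plan, followed exactly, gives no estimate or interval for the comparison that primary objective 2 asks for, and Protocol 12.1.2 promises intervals for an effect estimate that is never named.

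The size is moderate. The difference can be recovered from the planned tables, but its definition is left open until the data are known, and the planned display invites a reading that is too conservative by a factor of about 1.6 at SD 2.5 (4.62/2.91) and about 1.5 at SDs 6 and 4 (9.25/6.04). These figures assume 7 evaluable participants per group, one time point, no capped value and t-based intervals. The figures for change from T0 also rest on an assumed correlation. That the gap exists depends on none of these assumptions.

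**What to change.** 1. Add to SAP 5.5.3:

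> *For objective 2, the smoker minus never-smoker difference in mean STT at T0, T4, T8 and T12, and in mean change from T0 at T4, T8 and T12, will be presented with two-sided 95% Welch confidence intervals for FAS and PP. These are exploratory; no hypothesis is tested. If any STT value is capped at 60 minutes, the Hodges-Lehmann difference with its 95% CI will also be shown.*

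2. Add one column, Difference (95% CI), for each Visit 3 time point in Tables A 4 and A 5. While doing so, confirm that the change-from-T0 block has a row for the 95% CI that SAP 5.5.3 already promises. In the text available to me that block ends at Maximum, which may only reflect how the table was read.

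3. Record the addition in SAP section 6.

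The cost is three sentences, one column per Visit 3 time point in two table shells, and one line in section 6. No new data, visits or tests are needed.
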